8.0 Statistical Methods

8.1 General statistical conventions

All statistical procedures will be completed using SAS version 9.4 (or higher).

Continuous variables will be summarized using descriptive statistics, including number of subjects (n), mean, median, standard deviation (SD), interquartile ranges (IQR), minimum, and maximum.

For categorical variables, summaries will include counts of subjects and percentages. Percentages will be rounded to one decimal place.

For summary purposes, baseline will be defined as the last available pre-dose value. All summaries will be presented by treatment group, unless otherwise specified.

Immunogenicity titer data will be summarized using GMT/GMC and GMFR over baseline GMT/GMC. Immunogenicity data below the lower limit of quantification (LLOQ) will be summarized as LLOQ/2 in all relevant tables and will be displayed in listings in the format of source data. Immunogenicity data above the upper limit of quantification (ULOQ) will be summarized using ULOQ in all relevant tables and will be displayed in listings in the format of source data.

All subject data, including those derived, will be presented in individual subject data listings. Unless otherwise stated, unscheduled visit results will be included in date/time chronological order, within patient listings only. All listings will be sorted by subject ID, treatment group, study visit. Subject's sex and age will be also stated on each listing. Unless otherwise stated, data listings will be based on FAS.

Unscheduled data points will not be used in any summary tables separated by visit.

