8. STUDY ASSESSMENTS AND PROCEDURES

- Study procedures and their timing are summarized in the SoA (Table 2). Protocol waivers or exemptions are not allowed.
- Immediate safety concerns should be discussed with the Sponsor immediately upon occurrence or awareness to determine if the participant should continue or discontinue study intervention.
- Adherence to the study design requirements, including those specified in the SoA is essential and required for study conduct.
- All screening evaluations must be completed and reviewed to confirm that potential participants meet all eligibility criteria. The investigator will maintain a screening log to record details of all participants screened and to confirm eligibility or record reasons for screening failure, as applicable.
- Participants who experience any serious or severe AEs or any event of concern should be instructed to contact the study site and be scheduled for a visit for further evaluation. If an unscheduled visit occurs, the reason for the visit and data collected during the visit should be recorded and entered into the unscheduled eCRF.

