8.7 Safety analysis

This section describes the safety analyses that will be conducted during the active and follow-up periods (i.e., the safety analyses on all data collected during the active and follow-up periods and all data collected in subjects who dropped-out during the active and follow-up periods).

All definitions relative to safety endpoints are detailed in Section 4.4.

Safety analyses will be conducted on the safety population and will be performed for all safety variables specified below.

All safety data will be summarized by cohort and study visit as well as by overall study population.

The safety analyses of changes from baseline to a specific time point in safety variables (e.g., vital signs) will only include subjects from the safety population who have data available at both the baseline and the time point under considerations unless otherwise specified.

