8.7.2 Clinical laboratory evaluations

Clinical laboratory evaluations include serum chemistry, hematology and urinalysis. For the purposes of summarization in both the tables and listings, all laboratory values will be presented in SI units. If a lab value is reported using a nonnumeric qualifier e.g., less than (<) a certain value, or greater than (>) a certain value, the given numeric value will be used in the summary statistics, ignoring the nonnumeric qualifier. Severity of laboratory results will be categorized as mild, moderate, severe and potentially life threatening according to Appendices 2 - 4 in current document.

All laboratory data obtained between screening visit and the end of study will be used for the laboratory safety analysis. Frequencies and percentages of subjects with abnormal laboratory results will be summarized for each laboratory test and further by individual laboratory parameters at each time point. Shift tables for hematology and chemistry laboratory assessments between baseline and each subsequent visit will be provided if applicable.

Abnormal laboratory results will be listed by treatment group and visit, including patient information, lab parameter, lab results along with normal ranges, and abnormality criteria.

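### A graded laboratory abnormality seen only at an unscheduled visit may be missing from the laboratory summary tables: SAP 8.1 and 8.7.2 are not reconciled, and no worst-post-dose-grade table is named

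*SAP*

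**What the plan says.** SAP 8.1 sets two general rules for unscheduled results. The default is "Unless otherwise stated, unscheduled visit results will be included in date/time chronological order, within patient listings only". The second rule concerns tables: "Unscheduled data points will not be used in any summary tables separated by visit".

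SAP 8.7.2 then defines the data scope for laboratory safety: "All laboratory data obtained between screening visit and the end of study will be used for the laboratory safety analysis". It names two kinds of summary table. Abnormal results are to be "summarized for each laboratory test and further by individual laboratory parameters at each time point". Shifts are described as follows: "Shift tables for hematology and chemistry laboratory assessments between baseline and each subsequent visit will be provided if applicable". A listing of abnormal results, with normal ranges and abnormality criteria, is also planned. SAP 8.7 gives the general layout of the safety summaries: "All safety data will be summarized by cohort and study visit as well as by overall study population".

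Protocol 9.2.1 describes the grading shifts as running from baseline to every later measurement, which is wider than every later visit. SAP 9.0 declares no changes from the protocol analysis.

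The protocol creates unscheduled results in three ways. Section 8 has participants with serious or severe events, or any event of concern, "be scheduled for a visit for further evaluation", with the data entered on a separate unscheduled form. Section 8.3.1 has clinically significant laboratory values repeated until they resolve. Appendix 2 allows extra tests at any time.

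**The concern.** Laboratory incidence by cohort is normally read from the tables. Here the shift tables and the per-parameter abnormality counts are tied to visits or time points, and the general convention removes unscheduled values from tables of that form. Yet unscheduled draws are the ones taken when something looks wrong, so a participant's worst value could be one that the laboratory tables omit. Nor does the SAP settle how its two statements fit together. One programmer could follow SAP 8.1 and another the data-scope sentence in 8.7.2, and they would produce different counts. With 10 participants per cohort, one participant is enough to change the reported picture.

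**Working it through.** There is no power or sample-size figure to reproduce; SAP 5.0 says no formal calculation was made. The check sets the sections side by side and asks where a post-dose laboratory value from an unscheduled visit can appear.

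| Output | Source | Unscheduled post-dose value included? |
|---|---|---|
| Abnormal counts per parameter at each time point | SAP 8.7.2 | No, under SAP 8.1 |
| Abnormal counts for each laboratory test | SAP 8.7.2 | Unclear: may or may not be split by time point |
| Shift tables, baseline to each later visit | SAP 8.7.2 | No, under SAP 8.1 |
| Worst grade at any time after dosing | Not named in either document | Not applicable |
| Participant listings | SAP 8.1 | Yes |
| AE tables | SAP 8.7.1 | Only if the value is recorded as an AE |

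**The data-scope sentence.** Neither follow-up schedule (Protocol 1.2; SAP Table 3) contains safety laboratory tests. Laboratory data between the end of the Active Period and the end of study can therefore only be unscheduled. SAP 8.7.2 says data up to the end of study are used but, apart from the ambiguous per-test count, names no table that could hold them.

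**The AE route.** Protocol 8.3.1 and Table 8 make a laboratory change an AE when it is clinically significant, medically important, or needs intervention or added medication. SAP 8.7.1 summarises AEs by cohort, severity and relatedness, and counts a participant once per preferred term over the treatment period, so the by-visit rule does not remove them. The route is partial for three reasons:

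- It depends on the investigator's judgment and omits graded values judged not clinically significant.
- It carries an event term and an AE severity, not the laboratory grade.
- Footnote f of the schedule of activities limits AE collection to 4 weeks after each dose. On that reading, Weeks 4 to 8 in Cohort 2 and Weeks 4 to 12 in Cohort 3 are not covered for events that are not SAEs, AESIs or NOCIs. Protocol Table 5 reads more widely, from first dose to 4 weeks after the last dose.

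**Spacing of scheduled laboratory visits** (Protocol 1.2):

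- Day 8 to Day 29: 29 − 8 = 21 days.
- Day 64 to Day 85: 85 − 64 = 21 days.

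Each gap is 3 weeks, during which any value can come only from an unscheduled draw.

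**Size, for one participant whose only graded value is unscheduled:**

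- Cohort: 1/10 = 10.0% becomes 0/10 = 0%, a change of 10 percentage points.
- Overall: 1/30 = 3.3% becomes 0/30 = 0%, a change of 3.3 percentage points.

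**Baseline.** SAP 8.1 takes the last available pre-dose value and does not restrict it to scheduled visits, so an unscheduled pre-dose value can enter as baseline. The gap concerns post-dose values.

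**The case against.** A reader might infer that such a value reaches no summary table at all, and that a severe platelet fall between visits would be reported as no abnormality in the cohort. The documents do not support this. A clinically significant value becomes an AE and is tabulated. Thrombocytopenia and immune thrombocytopenia are listed as AESIs in Protocol Appendix 5, reportable from first dose to end of study under Table 5. A severe platelet fall would be expected in the AE tables even if the laboratory tables missed it.

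A reader might also infer that SAP 8.1 and 8.7.2 flatly contradict each other. The listings-only rule allows for exceptions stated elsewhere, and the data-scope sentence in 8.7.2 may be one. Laboratory analysis also includes listings, and the per-test count can be read as not split by visit. This is an unresolved conflict of wording, not a proven exclusion.

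Three further points on the other side have weight:

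- The exploratory laboratory endpoint (Protocol 3; SAP 4.3) concerns clinically significant abnormalities 1 week after each dose. Those are scheduled visits, and by-visit tables answer that endpoint.
- When a repeat follows an abnormal scheduled value, that scheduled value is already in the table. The repeat may still be worse, in which case the table shows the lower grade.
- All results are listed, and listings for 30 participants can be read in full. The table templates are in a separate document (SAP 1.0), so a worst-grade table could exist there.

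These points reduce the harm but do not settle the counting rule. Listings preserve the data without giving a cohort incidence, and an AE table could show an event for which the laboratory table shows nothing.

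**Conclusion.** The point holds in a limited form. Under the general rule in SAP 8.1, a graded abnormality seen only at an unscheduled visit is left out of the per-time-point counts and the shift tables, and SAP 8.7.2 does not say clearly whether it overrides that rule. The value is listed. It reaches the AE tables only if judged clinically significant or an AESI and, for other non-serious events, if it falls within the AE collection window. The values at risk are therefore mainly graded abnormalities judged not clinically significant and, on the narrower reading of the window, non-serious events more than 4 weeks after the first dose in Cohorts 2 and 3.

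The effect is 10 percentage points in a cohort's laboratory-table incidence, or 3.3 points overall, per participant missed. This assumes the planned 10 per cohort, no graded value for that participant at a scheduled visit, and no worst-grade table in the unseen templates. The documents give no basis for estimating how often this would happen. The SAP's shift description is also narrower than the protocol's while SAP 9.0 reports no change. The change is worth making because it is cheap and settles an ambiguity in safety counts.

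**What to change.** In SAP 8.7.2:

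1. State that unscheduled post-dose values count toward a table of worst post-dose grade per participant and parameter, by cohort and dose period.
2. Add one overall shift table from baseline to worst post-dose grade, using scheduled and unscheduled values, in line with the protocol's reference to every later measurement.
3. Define the dose periods so that every post-dose value falls in one, including values between Week 4 and the boost in Cohorts 2 and 3. Because the interval before the boost is 4, 8 or 12 weeks by cohort, footnote the unequal observation time.
4. Keep the by-visit tables, and the SAP 8.1 rule for them, unchanged.

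The cost is one extra table per laboratory panel (chemistry, hematology and urinalysis, so three) and one overall shift table. All of it uses data the protocol already collects; no visit, sample or data form changes.

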8.2 Subject disposition

Subject disposition information will be summarized by treatment group and overall. The number and percentage of subjects who are enrolled, who are eligible/ineligible to receive the second dose of vaccine, who complete the active period of the study, and who withdraw early from the study will be presented.

The primary reasons for ineligibility and early withdrawal will also be tabulated.

The number of subjects enrolled will be used as the denominator for the percentage calculation. Subject disposition will be listed.

The number and percentage of subjects in each analysis set will also be tabulated. A listing of each subject excluded from an analysis population will be listed as well as the reason why they were excluded from the population.

8.3 Protocol deviations

The number of subjects excluded from FAS, Safety, and Per-protocol analysis sets and reasons for exclusion will be summarized by treatment group and overall.

Population membership details will be listed, including reason for exclusion from each population.

Protocol deviation data are not captured in the clinical database and therefore will not be reported on individually within the scope of the SAP. Protocol deviations will be summarized in the final CSR.

8.4 Demographics and baseline characteristics

8.4.1 Demographics

Summary of demographics will be based on the FAS. Age at consent in years, height in cm, weight in kg and BMI (kg/m²) will be summarized descriptively using mean, SD, median, IQR, and range. Sex at birth, race and ethnicity will be summarized using frequencies and percentages.

8.4.2 Baseline and disease characteristics

The baseline continuous characteristics (vital signs) will be summarized descriptively for the safety population using mean, SD, median, IQR, and range. The baseline categorical characteristics (results of physical exam, chemistry, hematology and urinalysis) will be summarized (normal vs abnormal) using frequencies and percentages for the safety population.

8.4.3 Medical history

A summary of medical history will be presented by system organ class (SOC) and preferred term using the Medical Dictionary for Regulatory Activities (MedDRA) version 24.0 by cohort at baseline.

8.4.4 Prior and concomitant medications

Medications used in this study will be coded by using the World Health Organization Drug Dictionary Enhanced (WHODrug version March 1, 2021).

Concomitant medication is defined as any prescription or over-the-counter preparation. Use of concomitant medication from 4 weeks before Day 1 through 4 weeks after the last dose administration must be recorded in eCRF from the subject's medical file along with reason for use, dates of administration including start and end dates, dosage information including dose and frequency. Medications for pre-existing medical conditions or required for a medical condition during the study are allowed if not considered exclusionary. Medications specifically prohibited in the exclusion criteria (Section 5.2 in study protocol) are not allowed during the active study period, unless deemed medically necessary by the investigator. The Sponsor's medical monitor (or designee) should be contacted if there are any questions regarding concomitant or prior medications.

Concomitant medications will be summarized descriptively using frequency tables by Anatomical Therapeutic Chemical (ATC) class (hierarchically by Level I, II and III) and cohort in the descending order of overall frequency. All concomitant medications will be presented in listings as well.

Details for imputing missing or partial start and/or stop dates of medication are described in Section 7.3.

8.5 Extent of exposure

Vaccines will be administered on-site for all subjects. All subjects will receive the first dose on Day 1. Subjects will receive the second dose on Day 29 for Cohort 1 (4-week boost vaccination), Day 57 for Cohort 2 (8-week boost vaccination), and Day 85 for Cohort 3 (12-week boost vaccination), respectively, allowing for a potential delay up to 1 week. Frequencies and percentages will be calculated for the number of doses received (1 dose or 2 doses), the presence of delay in administering the second dose, whether vaccination is administered per protocol along with reasons why vaccine administration is not per protocol.

8.6 Immunogenicity analysis

This section addresses the analysis methods for immunogenicity outcomes.

8.6.1 Analysis methods

Immunogenicity will be evaluated using cellular and humoral immune function assays from blood and mucosal (saliva and nasal swab) samples. Samples will be collected from all subjects according to the time points specified in the SoE.

Results of the following immunogenicity assay results will be summarized descriptively by treatment group and visit and will be reported in the final CSR. Specific endpoints are listed in Sections 4.1 and 4.3.

- VP1 specific IgA ASC by ELISpot
- Norovirus G1.1 HBGA BT50
- VP1 specific serum IgG by ELISA or MSD
- VP1 specific IgG ASC by ELISpot
- VP1 specific serum IgA by ELISA or MSD

Additional exploratory endpoints will be evaluated and reported outside the scope of this SAP.

Kolmogorov-Smirnov test will be used to examine the normality assumptions of the immunogenicity assay results in log scale for each treatment group. If normality assumptions are met for all treatment groups, pairwise comparisons will be performed between treatment groups using Student t-test; Wilcoxon rank sum test will be used if otherwise.

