4.0 Study Endpoints

- 4.1 **Primary endpoints**
 - Number of VP1 specific IgA antibody secreting cells (ASC) by enzyme-linked immunospot (ELISpot) by treatment group and visit
 - Geometric mean titer (GMT) and geometric mean fold rise (GMFR) over the initial GMT of Norovirus G1.1 histo-blood group antigen (HBGA) blocking antibodies (BT50) by treatment group and visit
 - Geometric mean (GM) and GMFR over the initial results of VP1 specific serum IgG by Meso Scale Discovery (MSD) by treatment group and visit

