5.0 Sample Size and Power

No formal sample size calculation was performed for the study. Thirty subjects in total (10 in each cohort) are planned to be enrolled based on experience of a typical Phase I vaccine study.

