8.6.1.2 Analysis of Covariance (ANCOVA)

To account for the potential differences in baseline antibody level, ANCOVA will be used to analyze and compare the immunogenicity endpoints at each post-dose visits conditioning on baseline values for the Norovirus G1.1 HBGA BT50 assay. Separate models will be estimated at each post-dose visit, using log titer as a dependent variable, treatment group as a factor and baseline log titer as a covariate. LSMs for each cohort and differences in LSM between cohorts will be estimated from each model along with 95% CIs. Both LSMs for each cohort and the differences in LSM between cohorts along with their 95% CIs will be exponentiated to the original scale, resulting geometric LSMs for each cohort and LS-GMR between cohorts. In order to compare immunogenicity assay results among treatment groups, significance on 28 days post the second dose, pairwise comparisons will be performed.

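### An under-specified Kolmogorov-Smirnov pre-test on about 10 subjects per cohort picks the only between-cohort test for IgA ASC and serum IgG, so method and estimand are not fixed in advance

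*SAP*

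**What the plan says.** SAP 8.6.1 lists five assays, including the three primary ones (IgA ASC, BT50, serum IgG). After descriptive summaries it adds a two-stage rule. First, a "Kolmogorov-Smirnov test will be used to examine the normality assumptions of the immunogenicity assay results in log scale for each treatment group". The t-test is the choice only when all three cohorts pass. When any cohort fails, the alternative applies: "Wilcoxon rank sum test will be used if otherwise". One failing cohort is therefore enough to move the comparison to Wilcoxon.

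SAP 8.6.1.2 adds, for BT50 only, that "ANCOVA will be used to analyze and compare the immunogenicity endpoints at each post-dose visits", with cohort as factor and baseline log titer as covariate. This analysis does not depend on the pre-test. Pairwise testing under it is stated for 28 days after dose 2. SAP 4.2 lists the resulting BT50 ratio between cohorts as a secondary endpoint. No such ratio is listed for IgA ASC or serum IgG.

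On size, SAP 5.0 says "Thirty subjects in total (10 in each cohort) are planned to be enrolled" and "No formal sample size calculation was performed for the study". The protocol names no between-cohort test.

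**The concern.** The data that are to be compared also choose the test. With about 10 values per cohort, a normality test often fails to see real non-normality and sometimes reports it where there is none. The two branches answer different questions: a log-scale t-test addresses a ratio of geometric means, and Wilcoxon a shift in ranks. Two of the three primary assays have no other comparison between cohorts, so what will be estimated is unknown until the data are in.

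Three gaps add to this. The SAP does not say whether the test is corrected for a mean and SD estimated from the sample. It gives no level for the test. It does not say whether the choice is made once, per assay, or per assay and visit. The last gap has a practical side: under the SAP schedule, serum is taken from Cohorts 1 and 2 only on Day 57, Cohorts 2 and 3 only on Day 85, and Cohort 3 alone on Day 113. A condition on all groups has no clear meaning at those visits.

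**Working it through.** The plan states no power or error rate for this rule, so there is no figure to reproduce.

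**Inputs from the documents.** Three cohorts of 10 (SAP 3.1 and 5.0; one sentence in protocol 9.1 gives 30 per arm but also 30 in total, and every other place gives 10). Earlier IgA ASC mean 560 and SD 740, N=23, at a different dose level (protocol 9.1), used only to choose one plausible shape. Values below LLOQ set to LLOQ/2 (SAP 8.1).

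**Assumed.** Two-sided 5% for all tests, and the distribution shapes below.

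**Step 1: false switching with truly log-normal data.** With a corrected test at level a in three independent cohorts, P(switch) = 1 − (1 − a)^3.
- a = 0.01: 3.0%
- a = 0.05: 1 − 0.95^3 = 14.3% (simulated 14.0%)
- a = 0.10: 27.1%
- a = 0.15: 38.6%

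If the rule is applied to each of the three primary assays at one visit, and the assays are independent (an assumption), the chance that at least one switches at a = 0.05 is 1 − 0.95^9 = 37%.

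**Step 2: switching by true shape.** Simulation with 40,000 trials per shape, n=10 in each of three cohorts. The 5% critical value of D is 0.262 if corrected for estimated mean and SD, and 0.409 from plain tables.

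| Shape on log scale | One cohort fails, corrected | Any of three fails, corrected | Any of three fails, plain tables |
|---|---|---|---|
| Normal | 4.9% | 14.0% | 0.01% |
| 50/50 mixture, 3 SD apart | 7–8% | about 20% | under 0.01% |
| 30% non-responders, 3 SD lower | 10.1% | 27.3% | 0.02% |
| Log of an exponential | 11.6% | 31.1% | 0.1% |
| 20% at a floor | 15.3% | 39.1% | 0.3% |
| t with 3 df | 15.8% | 40.4% | 1.7% |
| Log of gamma with mean 560, SD 740 | 15.9% | 40.5% | 0.3% |
| 30% censored to LLOQ/2 | 19.8% | 48.3% | 2.7% |
| Exponential | 30.0% | 65.6% | 1.2% |

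The rule acts on the three-cohort column. Under the corrected version, one and the same distribution can lead to either test. Under plain tables, the t-test is chosen almost always.

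**Step 3: error rate and power.** These use the corrected version. Type I error of the whole two-stage rule is 4.6–5.2% across the simulated shapes. Given the branch chosen, it ranges from 2.6% to 6.8%. With normal log data and an assumed 1.3 SD shift, power is 78.5% (fixed t-test), 74.0% (fixed Wilcoxon) and 78.0% (two-stage). In the non-normal shapes, two-stage minus fixed t-test runs from 74.4 − 78.5 = −4.1 points (30% censored) to 85.1 − 79.4 = +5.7 points (exponential). The t-test and Wilcoxon disagree at p<0.05 in about 2% of null trials and 7–11% of trials with that shift.

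**Step 4: BT50 and baseline adjustment.** At 28 days after dose 2, SAP 8.6.1 and 8.6.1.2 both give pairwise p-values. With baseline correlation 0.5–0.7 and a shift of 1.0–1.3 SD (all assumed), ANCOVA and the t-test fall on opposite sides of 0.05 in 14–32% of trials. At 1.0 SD, adjustment raises power from about 56% to 66–81%. Serum IgG has a Day 1 sample and would gain in the same way, but no adjustment is planned for it.

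**The case against.** The best defence is that the rule is written down in advance, leaves the analyst little discretion and does not distort error rates. That is right: 4.6–5.2% type I error and 78.0% against 78.5% power are no cause for alarm. The study is also non-randomised (SAP 3.2) and has no sample size calculation, and no development decision is tied to these p-values. This limits how much the point matters.

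A reader might go further in several ways that the documents do not support:
- **Inflated false positives.** Step 3 shows none of note.
- **Frequent false switching together with near-zero detection.** These belong to different versions of the test. Corrected, false switching is 14% at the 5% level; uncorrected, detection is at most 2.7% and switching all but disappears. Only one can apply.
- **A choice made separately for every assay and visit.** This is a natural reading, because the endpoints are by visit, but the SAP does not say so.
- **Loss of ratio and CI when Wilcoxon is chosen.** Per-cohort geometric means and fold rises with 95% CIs are planned for BT50 and serum IgG whichever test is used (SAP 4.1 and 7.1). BT50 has an adjusted ratio with CI regardless. The t-test branch promises no ratio either.
- **Two sets of BT50 p-values at every visit.** ANCOVA estimates and CIs are planned at each visit, but pairwise testing is explicit only at 28 days after dose 2.

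It can also be argued that BT50 already has an order, since titers and fold rises are primary and the ANCOVA ratio secondary. But the primary items are summaries by cohort, not contrasts, and no section says which p-value governs. The Holm adjustment in SAP 8.6.2 works across cohort pairs and does not settle this.

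**Conclusion.** The concern holds as one of specification. For IgA ASC and serum IgG, the sole between-cohort comparison depends on a pre-test whose version, level and scope are unstated. The omission of the version alone decides between a rule that switches in 14% of log-normal cases and about 20–66% of clearly non-normal ones, and a rule that does almost nothing. The consequences are an estimand that is not fixed, no planned ratio with CI between cohorts for those two assays, no baseline adjustment for serum IgG, and two unranked BT50 comparisons at 28 days after dose 2.

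The switching figures rest on the assumed shapes and, except for the range of levels in step 1, on an assumed 5% level. The 37% figure also assumes independent assays, and the BT50 figures rest on assumed baseline correlations. The change is worth making because the study exists to compare boost intervals and costs little to put right, not because its error rates are at risk.

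**What to change.** - Delete the normality pre-test from SAP 8.6.1.
- Name log-scale ANCOVA (cohort plus baseline log value, as already planned in SAP 8.6.1.2) as the between-cohort analysis for BT50 and serum IgG. State that it governs for BT50.
- Name a log-scale t-test for IgA ASC, whose primary endpoint is a count with no fold rise defined.
- Report the geometric mean ratio with 95% CI for each cohort pair, and define the comparison visit by days since dose so that the cohorts line up.
- Give Wilcoxon for every endpoint as a fixed sensitivity analysis. Because it uses ranks, it does not depend on the value substituted below LLOQ.

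Data-driven switching then falls to zero. With normal log data no power is lost (78.5% against 78.0%). With heavy-tailed or right-skewed log data the fixed t-test gives up roughly 5–6 points at a 1.3 SD shift, which the Wilcoxon result would show. Baseline adjustment improves precision but does not remove confounding from non-random cohort assignment.

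The cost is small: edits to SAP 8.6.1, 8.6.1.2 and the endpoint list in 4.2, and one added ANCOVA for serum IgG. Nothing changes in study conduct or sampling.
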